Study Endpoints:	Primary endpoint:					
	 The primary endpoint for the cardiodynamic ECG assessment is the placebo-corrected change from-baseline QTcF (ΔΔQTcF). 					
	Secondary endpoints:					
	 Change-from-baseline QTcF, PR, QRS, and heart rate (HR) (ΔQTcF, ΔPR, ΔQRS, and ΔHR) 					
	 Placebo-corrected ΔPR, ΔQRS and ΔHR (ΔΔPR, ΔΔQRS, and ΔΔHR) 					
	Categorical outliers for QTcF, HR, PR, and QRS					
	Frequency of treatment emergent changes of T-wave morphology and U-wave presence					
	 The PK endpoints will include the plasma and urine PK parameters for ITF2357, ITF2374, ITF2375, ITF2440, ITF2563, ITF2955 glucuronide, and moxifloxacin (as described in the Pharmacokinetics section). 					

	 Safety and tolerability to ITF2357 will be evaluated through the assessment of adverse events (i.e., seriousness, severity, relationship to the study medication, outcome, duration, and management), vital signs, ECG, and clinical laboratory parameters.
Pharmacokinetics:	Parameters for plasma PK: AUC_{0-t} , AUC_{0-12} , AUC_{0-inf} , Residual area, C_{max} , T_{max} , $T_{\% el}$, and K_{el} , CL/F , and Vd/F .
	Parameters for urine PK: A _{e0-t} , R _{max} , T _{Rmax} , and Clr.
Statistical Analyses:	Cardiodynamic ECG assessment:
	The primary analysis will be based on concentration-QTc modeling of the relationship between plasma concentrations of ITF2357 and change-from-baseline QTcF (Δ QTcF) with the intent to exclude an effect of placebo-corrected Δ QTcF (Δ Δ QTcF) >10 msec at clinically relevant plasma levels.
	In addition, the effects of ITF2357 on the placebo-corrected $\Delta QTcF$, ΔHR , ΔPR , and ΔQRS ($\Delta \Delta QTcF$, $\Delta \Delta HR$, $\Delta \Delta PR$, and $\Delta \Delta QRS$) will be evaluated at each post-dosing time point ('by time point' analysis). An analysis of categorical outliers will be performed for changes in QTcF, HR, PR, QRS, T-wave morphology and U-wave presence.
	Assay sensitivity will be evaluated by concentration-QTc analysis of the effect on $\Delta\Delta QTcF$ of moxifloxacin using a similar model as for the primary analysis. Assay sensitivity will be deemed as met if the slope of the concentration-QTc relationship/ $\Delta QTcF$ is statistically significant at 10% level of significance in a 2-sided test and the predicted QT effect (i.e. the lower bound of the 2-sided 90% confidence interval [CI] of $\Delta\Delta QTcF$) is above 5 msec at the observed geometric mean C_{max} of 400 mg moxifloxacin.
	Pharmacokinetic assessment:
	Individual and mean plasma concentration versus time curves will be presented for both linear and semi-log scales. Descriptive statistics (arithmetic and geometric means, standard deviation [SD], coefficient of variation [CV%], minimum [Min], maximum [Max], and median) of the plasma concentrations versus time will be presented as well for the pharmacokinetic parameters.
	Safety assessments:
	Treatment-emergent adverse events (TEAEs) will be tabulated by treatment for all subjects who were dosed (Safety Population). Changes from baseline values in vital signs, ECG, and clinical laboratory parameters will be evaluated and tabulated by study treatment. Safety and tolerability data will be reported using descriptive statistics. Demographic parameters will be summarized descriptively.
	Adverse events of special interest:
	The rates of adverse events of special interest (AESI) should be compared in the treatment and control period. Subgroup analyses should be conducted in terms of age, gender, pre-existing cardiac disease, electrolyte disturbances and concomitant medications.
	Details of statistical analyses will be developed in a Statistical Analysis Plan (SAP) that will be prepared after completion of the final protocol.

3. List of Abbreviations and Definition of Terms

ADR adverse drug reaction

AE adverse event

AESI adverse events of special interest

Ae_{0-t} cumulative urinary excretion from time zero to time t

ALT Alanine Aminotransferase

AMIS Analytical Methodology Information Sheet

AST Aspartate Aminotransferase

AUC area under the curve

b.i.d. twice a day

BMI body mass index BP blood pressure

CI confidence interval

CFR Code of Federal Regulations

Clr renal clearance

Cl/F apparent total body clearance C_{max} maximum plasma concentration

CRF Case Report Form

CTA Clinical Trial Application

CTCAE National Cancer Institute Common Terminology Criteria for Adverse Events

CTMS Clinical Trial Management System

CV coefficient of variation

CYP cytochrome P450

DNA deoxyribonucleic acid EDC electronic data capture

ECG electrocardiogram

EMA European Medicines Agency
FDA Food and Drug Administration

GCP Good Clinical Practice
GLP Good Laboratory Practice
GMP Good Manufacturing Practice

HBsAg hepatitis B surface antigen

HCV hepatitis C virus
HDAC histone deacetylase
HDL high-density lipoprotein

HEENT head, eyes, ears, nose, and throat

hERG human ether-go-go-related gene HIV human immunodeficiency virus

HR heart rate

ICF Informed Consent Form IB Investigator's Brochure

ICH International Council for Harmonisation of Technical Requirements for

Pharmaceuticals for Human Use

IC50 concentration at which 50% inhibition observed

ID identification

IEC Independent Ethics Committee IRB Institutional Review Board

IV intravenous

K_{el} elimination rate constant

kg kilogram L liter

LDL low-density lipoprotein

LIMS Laboratory Information Management System

LQTS long QT syndrome

M moxifloxacin

mARC mitochondrial amidoxime reducing components

Max. maximum

MedDRA Medical Dictionary for Regulatory Activities

MDMA 3,4-methylenedioxymethamphetamine

mg milligram

Min. minimum

min minute

mL milliliter

mmHg millimeters of Mercury
NOL No Objection Letter

NYHA New York Heart Association

OT oral temperature OTC over-the-counter

P placebo

PCP phencyclidine

PD pharmacodynamic(s) PK pharmacokinetic(s) PR PR interval of the ECG
PTT partial thromboplastin time

PT prothrombin time
QA quality assurance
QC quality control

QRS QRS interval of the ECG QT QT interval of the ECG

QTcF Fridericia's corrected QT interval
R_{max} maximum rate of urinary excretion

RR RR interval of the ECG

RR respiratory rate

SAE serious adverse event SAP Statistical Analysis Plan

SARS severe acute respiratory syndrome

SD standard deviation SE standard error

SOP Standard Operation Procedure

ST supratherapeutic dose

SUSAR suspected unexpected serious adverse reaction

T therapeutic dose

TEAE treatment-emergent adverse event

TdP torsade de pointes
t.i.d three times a day
T1/2 el elimination half-Life

 T_{max} time of maximum concentration T_{Rmax} time of maximal urinary excretion

US United States

Vd/F apparent volume of distribution

WBC white blood cell

Δ change from baseline

ΔΔ placebo-corrected change from baseline

4. Schedule of Events

[figure not shown]
		Periods 1, 2, 3 and 4						
PROCEDURE	Screening D -28	D-1	D1	D2	D3	D4	Study Exit/Early Termination ¹	Follow-up Telephone Call (Day 12±2 days)
Inform Consent Form	X							
Inclusion and exclusion criteria check ²		X						
Randomization ²		X						
Demographic Data ³	X							
Medical and Medication Histories	X							x
Review and Monitoring of AEs, and Concomitant Medications	x	x	x	x	x	X	x	x
Physical Examination ⁴	X	X		X		X	X	
Body Measurements (Height, Weight, and BMI)	X	X ⁵						
Supine Vital Signs (BP, HR, RR, OT)	X		X ⁶	X ⁶			X	
12-lead Safety ECG	X		\mathbf{X}^7	X^7			X	
Continuous ECG (Holter Monitoring)			X8	X8				
Hematology	X	X ⁹		X^9		X ⁹	X	
Biochemistry	X	X ⁹		X ⁹		X ⁹	X	
Coagulation	X	X^9		X^9		X^9	X	
Serology (HIV and Hepatitis B and C)	X							
Urinalysis	X	X^9		X^9		X^9	X	
Urine Drug Screen	X	X						
Urine Cotinine Test	X	X						
Alcohol Breath Test	X	X						
Serum Pregnancy Test		X						
Urine Pregnancy Test	X					X	X	
Confinement ¹⁰		X	X	X	X	X		
Study Treatment Administration (ITF2357 [T or ST], Moxifloxacin [M] or Placebo [P]) ¹¹			х					
Plasma PK Samples ¹²			X	X	X	X		
Urine PK Samples ¹³			X	X	X	X		

[figure not shown]
Study procedures performed on Day 4 of Period 4 will serve as study exit procedures. Early termination procedures will be performed as soon as possible after subject withdrawal, always within 14 days after last participation of the subject in the study. If clinically significant abnormal results are found on the laboratory assessments performed during Study Exit/Early Termination, the subject will be invited to the site clinic again to repeat abnormal parameters.

² Randomization, inclusion and exclusion criteria check to be performed at check-in on Day -1 of Period 1.

- 3 Demographic data including: age, sex, race, and ethnicity.
- A complete physical examination (head, eyes, ears, nose, throat (HEENT), neck (including thyroid), chest, lungs, abdomen, back, lymph nodes, musculoskeletal, dermatological, cardiovascular/peripheral vascular, and general neurological examination) will be performed at screening and at study exit. In Periods 1, 2 and 3, a brief physical examination will be performed at check-in on Day -1, and approximately 24 (Day 2) and 72 (Day 4) hours post-dose. In Period 4, a brief physical examination will be performed at check-in on Day -1 and approximately 24 hours post-dose. A brief physical examination will consist of: HEENT, chest, lungs, abdomen, dermatological, cardiovascular/peripheral vascular, and areas of note elicited from the subject.
- 5 Body weight, will be determined at check-in on Day -1 of each period.
- 6 Supine vital signs (BP, HR, RR and OT): pre-dose (Day 1), and approximately 2, 3, 6, 12, and 24 hours post-dose. Vital signs will be matched to the 12-lead safety ECG. Blood pressure measurement: two measures performed after at least 5 minutes of resting in supine position, measures 2 minutes apart from each other.
- 7 12-lead safety ECG: pre-dose (Day 1) and approximately 2, 3, 6, 12, and 24 hours post-dose. 12-lead safety ECG will be matched to vital signs.
- 8 Continuous ECG: Subjects will be continuously monitored from approximately 1 hour pre-dose (Day 1) until approximately 36 hours post-dose. Extraction time points for ECG are: -45, -30 and -15 minutes pre-dose and 0.5, 1, 1.5, 2, 2.5, 3, 3.5, 4, 5, 6, 7, 8, 12, 24, and 36 hours post-dose. The ECG extraction time points will be paired with PK determinations. Subjects will be supinely resting for at least 10 minutes before and 5 minutes after each time point, whenever possible.
- 9 Fasting safety laboratory assessments (i.e., biochemistry, hematology, urinalysis and coagulation): at check-in on Day -1, and 24 (Day 2) and 72 (Day 4) hours post-dose.
- 10 Subjects will be confined from at least 12 hours pre-dose on Day -1 until after 72 hour post-dose assessments on Day 4.
- 11 Study drug administration should be documented along with confirmation of the total dose being administered.
- 12 Blood samples for ITF2357 and metabolites, and moxifloxacin PK: pre-dose and 0.5, 1, 1.5, 2, 2.5, 3, 3.5, 4, 5, 6, 7, 8, 12, 24, 36, 48, 60 and 72 hours post-dose (6 mL for each sampling time for study treatments S, ST, and P; 3 mL for study treatment M).
- 13 Urine samples for PK: spot pre-dose (within 2 hours before dosing), 0-8 hours, 8-24 hours, 24-48 hours, and 48-72 hours post-dose.

5. Introduction

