12.4.4 Adverse Events of Special Interest

The rates of these AESI should be compared in the treatment and control period. Subgroup analyses should be conducted in terms of age, gender, pre-existing cardiac disease, electrolyte disturbances and concomitant medications.

13. Regulatory Considerations and Quality Assurance

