### 4. Change From the Protocol

No changes in planned analyses were done compared to the protocol.

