### 9.2 Adverse Events

AEs will be recorded and evaluated for their seriousness, severity, and relationship to the study medication. Adverse events will be collected and documented during the course of the study,

from ICF signature until a period of  $12\pm 2$  days following the last study drug administration, and they will be followed-up until complete resolution, or until the Investigator judges it to be safe to discontinue follow-up.

Treatment-emergent AEs and non-TEAEs (those occurring prior to administration of study medication or that first occurred prior to study drug administration and did not worsen in frequency or severity) will be listed. TEAEs will be defined as AEs that occur on or after the date and time of study drug administration, or those that first occur pre-dose but worsen by increase in occurrence or severity after study drug administration.

The incidence of TEAEs will be summarized using the safety population. The updated version of MedDRA® dictionary will be used to classify all AEs reported during the study by SOC and PT.

Incidence of subjects who experienced TEAEs will be presented by treatment and overall, SOC, PT, by Investigator-assessed relationship and also by severity. Each subject may only contribute once to each of the incidence rates, for a TEAE following a given treatment, regardless of the number of occurrences; the highest severity or highest relationship will be presented, as appropriate. In each table, SOC will be presented in descending order of overall incidence rate in terms of frequency of subjects and then in frequency of events (alphabetical order will be used in case of equal rates). For each SOC, PT will be presented the same way.

Incidence of TEAEs (number of events) will also be presented by treatment and overall, by SOC, and PT, by Investigator-assessed relationship and severity.

Frequency of subjects experiencing Serious Treatment Emergent Adverse Events and Suspected Unexpected Serious Adverse Drug Reactions; and the number of events would be also summarized per treatment and overall. Also, these events and Serious Adverse Events will be listed per subject.

The severity of AEs will be assessed and graded according to the most recently published National Cancer Institute Common Terminology Criteria for AE (CTCAE).

The relationship of an AE or SAE to the study drug will be assessed according to the study protocol as:

- Related to study drug;
- Not related to study drug;
- Unknown.

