### 9.2.1 Adverse Events of Special Interest

Adverse events of special interest (AESIs) for this study will include the following:

- Torsade de pointes;
- Sudden death;
- Ventricular tachycardia;
- Ventricular fibrillation and flutter;
- Post-dose syncope ;
- Seizures.

Which are to be classified as AESI in the CRF and will be recorded from ICF signature and throughout the study period until study completion. When these events are identified they should be examined closely for other risks factors, and evaluated. Also the need for evaluation by a cardiac specialist will be discussed by the Investigator and the Sponsor.

Incidence of AESIs (number of events) will also be presented by treatment and overall for severity and relationship and by treatment and overall for age, gender, pre-existing cardiac disease, electrolyte disturbances and concomitant medications.

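### SAP 9.2.1 tabulates AESIs as event counts only, so no subject-level AESI rate, combined or by subgroup, is planned for the comparison the protocol asks for

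*Protocol*

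**What the plan says.** The protocol asks for AESI rates to be compared in its synopsis ("The rates of adverse events of special interest (AESI) should be compared in the treatment and control period") and again in section 12.4.4 ("The rates of these AESI should be compared in the treatment and control period"). Section 12.4.4 adds: "Subgroup analyses should be conducted in terms of age, gender, pre-existing cardiac disease, electrolyte disturbances and concomitant medications".

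SAP 9.2.1 provides one AESI display: "Incidence of AESIs (number of events) will also be presented by treatment and overall for severity and relationship". The same sentence extends the display "by treatment and overall for age, gender, pre-existing cardiac disease, electrolyte disturbances and concomitant medications". It mentions no number or percentage of subjects and no denominator, and it does not say which treatment is the control. SAP 4 states: "No changes in planned analyses were done compared to the protocol".

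The general adverse event section, SAP 9.2, does more: "Incidence of subjects who experienced TEAEs will be presented by treatment and overall, SOC, PT, by Investigator-assessed relationship and also by severity". There each subject counts once per treatment, the Safety Population is used, and event counts come as a separate, additional display. Serious TEAEs likewise get both a subject frequency and an event count.

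**The concern.** The protocol's word is rates. An event count is not a rate, because it has no denominator and because a subject with repeat episodes counts several times. AESIs here are arrhythmias, sudden death, syncope and seizures, and episodes of some of these can recur in one person within a period. With few events expected, one such subject could dominate the display.

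At stake is whether the report shows directly what share of subjects had an AESI on the therapeutic dose (T) and the supratherapeutic dose (ST) compared with control, overall and within the five subgroups. The rates can be partly recovered from other tables, but the SAP does not plan them, and SAP 4 does not tell the reader that rates have become counts.

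**Working it through.** The plan gives no figure to reproduce on this point. The check compares the sections and adds a short illustration.

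**1. Subject counts and event counts in the SAP**
- TEAEs (SAP 9.2): subjects, then events.
- Serious TEAEs and SUSARs (SAP 9.2): subjects and events.
- AESIs (SAP 9.2.1): events only.

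The SAP treats these as two measures elsewhere, so the event count cannot be read as shorthand for a subject rate.

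**2. Does an event count fix the rate?**

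Inputs: up to 34 subjects enrolled (protocol 8.1), taken as all dosed; three AESI events on one treatment (assumed). Rate = subjects with at least one AESI / subjects dosed.
- Three events in one subject: 1/34 = 2.9%
- In two subjects: 2/34 = 5.9%
- In three subjects: 3/34 = 8.8%

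In a subgroup of 10 (assumed), the same three events give 1/10 = 10%, 2/10 = 20% or 3/10 = 30%. The planned display shows 3 in every case.

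**3. Can the TEAE tables in SAP 9.2 replace it?**

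For a single preferred term, yes: those tables give affected subjects by treatment. For AESIs combined, no. Suppose the ST column shows one subject with syncope and one with ventricular tachycardia. If they are the same person, the combined rate is 1/34 = 2.9%; if they are two people, it is 2/34 = 5.9%. The rows are identical, so they cannot be summed.

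**4. Subgroups**

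The TEAE tables are not split by the five factors, so no subject-level AESI rate is planned in any subgroup. Denominators are only partly available elsewhere:
- Age group and sex are tabulated (SAP 8.3).
- Medical history is summarised by treatment (SAP 8.4), but no rule says what counts as pre-existing cardiac disease.
- Concomitant medications are only listed (SAP 8.5).
- Electrolyte disturbance has no subgroup definition.

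The last two can change from one period to the next, so their denominators need not match across treatments even in a crossover.

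**5. How much could this matter?**

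If the true risk were 1% per treatment (assumed), the chance of any affected subject among 34 is 1 − 0.99^34 = 28.9%, so an empty column is the likelier result. With zero affected, the one-sided 95% upper bound is 1 − 0.05^(1/34) = 8.4%. Any comparison will be sparse.

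**The case against.** SAP 9.2.1 sits under 9.2, and its word for the event counts is that they will also be presented, which can be read as adding to the subject-level tables just above. AESIs are adverse events with preferred terms, so treatment-emergent cases appear there once per subject and treatment. In a four-period crossover each subject is due to receive every treatment, so denominators are nearly equal apart from dropouts and missed periods. Adverse events are also listed, so combined counts could be built by hand. Table shells are in a separate document that is not available here and may already print N and percentages. The protocol leaves analytical detail to the SAP, both documents confine safety to description, and exclusion criteria 4 and 6 should leave the cardiac disease subgroup almost empty.

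Most of this stands, and it settles the severity. It does not close the gap. The tables that the SAP adds to have no combined AESI row and no subgroup split, and any percentages in the shells should have their basis in the SAP text.

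A reader might infer more than the documents support:
- **That the comparison cannot be made at all.** The preferred-term tables allow it term by term across treatments.
- **That pre-dose AESIs enter the overall column**, because AESIs are "recorded from ICF signature and throughout the study period until study completion". That is a collection rule. SAP 9.2 separates TEAEs from non-TEAEs, and nothing says pre-dose events are tabulated with the rest.
- **That the overall column is an error because it includes moxifloxacin.** An overall column is the SAP's general safety convention, and the by-treatment columns remain separate.
- **That rates should be taken over the 28 evaluable subjects.** The Safety Population is everyone dosed.

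**Conclusion.** The point holds as a minor one. The protocol asks for AESI rates to be compared, with subgroups, while SAP 9.2.1 specifies only event counts and SAP 4 declares no change. A term-by-term comparison of subjects across treatments is available from SAP 9.2. What is not planned is a subject-level rate for AESIs combined or for any subgroup.

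The size depends on how events cluster within subjects. In the illustration, the same count of three fits rates from 2.9% to 8.8% of 34 dosed subjects, and from 10% to 30% in a subgroup of 10. The three events and the subgroup size are assumptions; 34 is the enrolment ceiling, with all taken as dosed. If no AESI occurs, subject and event counts agree and only the denominator is missing. The primary QTc analysis and the assay sensitivity conclusion are unaffected.

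The control period is also unnamed. Placebo and moxifloxacin are both comparators, so the SAP should say which is meant. This is a matter of clarity, since a by-treatment display serves either reading.

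**What to change.** In SAP 9.2.1:
- Make the main display the number and percentage of subjects with at least one treatment-emergent AESI, out of Safety Population subjects dosed with that treatment.
- For each subgroup, give the same figures out of subjects in that subgroup dosed with that treatment. Printing this N requires a short definition of each subgroup level.
- Show T and ST each beside placebo, with moxifloxacin in its own column.
- Keep event counts as a second column.
- State which period is the control, and that the comparison is descriptive.

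The cost is SAP wording and one table shell. No new data are needed. If the shells already carry n/N (%), only the SAP text changes.

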5.2 Moxifloxacin Background Information

[figure not shown]
Moxifloxacin is a synthetic fluoroquinolone with a broad spectrum of activity and a bactericidal mode of action. Moxifloxacin is indicated for the treatment of adults with bacterial infections caused by susceptible strains of the designated microorganisms for which treatment is appropriate. The recommended dose for moxifloxacin is 400 mg once daily for all indications. The duration of therapy and route of administration is dependent upon the type and severity of infection.²

[figure not shown]
The bactericidal action results from the interference of moxifloxacin with bacterial topoisomerases II (DNA gyrase) and IV.²

Moxifloxacin prolongs the QTc interval, an effect that is believed to occur through inhibition of the I_{Kr} hERG channel in the cardiac myocyte.³

Moxifloxacin given as an oral tablet is well absorbed from the gastrointestinal tract. The absolute bioavailability of moxifloxacin is approximately 90%. Following oral administration, peak plasma concentration is attained in 1 to 3 hours. Plasma concentrations increase proportionately with dose up to the highest dose tested (1200 mg single oral dose).²

Moxifloxacin is approximately 50% bound to serum proteins, independent of drug concentration. Moxifloxacin is metabolized via glucuronide and sulfate conjugation. The cytochrome P450 system is not involved in moxifloxacin metabolism, and is not affected by moxifloxacin. Moxifloxacin is eliminated from plasma by first-order process. The mean (±SD) elimination half-life from plasma is 12±1.3 hours.²

